6.3 Secondary Endpoints

The secondary endpoints of this registry are:

1. Secondary efficacy rate, defined as the percentage of soft tissue lesions that have undergone successful repeat ablations (target or non-target) following identification of local soft tissue lesion progression. A successful repeat ablation will be defined as ablation of the lesion according to the protocol and covered completely, with an adequate margin, as defined by the performing physician (i.e. the ablation zone completely overlaps or encompasses the lesion plus an ablative margin), as assessed by CT, MRI, PET, US, and/or X-ray, immediately following the procedure.
2. Regional recurrence rate at a separate location in the liver (outside the initial treatment site(s)), evaluated at every visit after ablation of the target lesion(s), and overall evaluation at the 5-year follow-up, as assessed by CT, MRI, PET, US, and/or X-ray.
3. Recurrence-free survival, evaluated at every visit after ablation of the target lesion(s), and overall evaluation at the 5-year follow-up, as assessed by CT, MRI, PET, US, and/or X-ray.
4. Overall survival, evaluated at every visit after ablation of the target lesion(s), and overall evaluation at the 5-year follow-up.
5. Assess economic impact of ablation by capturing procedure-related items such as: complete procedure duration, ablation duration, number of ablations, length of hospital stay, and number and types of probes used.
6. Incidence of adverse events (AEs) (SAEs) that are deemed at least unlikely related to the procedure or device and all serious adverse events (SAEs) from the start of the ablation procedure through the end of the study.
7. Two QOL questionnaires: European Organization for Research and Treatment of Cancer (EORTC) QLQ-C30 and liver-specific QLQ-HCC18.

Note: These two questionnaires were chosen as tools to assess overall health status/quality of life in the patient population with soft-tissue liver lesions.

8. Numeric Pain Rating Score.

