12.3 Post-ablation Follow-up Visits

The list of assessments is the same for all follow-up visits unless otherwise specified.

At each follow-up visit, the patient will visit the site (or have a tele-visit and/or phone visit when unable to visit the site) and the following assessments will occur:

- Evaluate ECOG performance status (Visit 3 only). After Visit 3, evaluate ECOG, if applicable per site SOC. ECOG may be assessed over the phone.
- Laboratory tests, as follows, if applicable per site SOC:
 - Coagulation tests, including, INR, PT and APTT (or PTT).
 - Liver function tests, including AST, ALT, GGT, albumin, direct and total bilirubin, and total protein.
 - Renal function tests, including BUN, creatinine and electrolytes (sodium, potassium, chloride and bicarbonate).
 - CBC, including differential cell count and platelet count.
 - Genetic markers including: Alpha-fetoprotein (AFP) level, Carbohydrate antigen 19-9 (CA19-9) level, Carcinoembryonic antigen (CEA).
- Record all relevant concomitant medications: Relevant concomitant medications include: chemotherapy, immunotherapy, blood-thinning or coagulation, NSAIDs, those medications used to treat AEs, those used for hepatitis (if concurrently treating), and any others that are relevant in the opinion of the investigator. Relevant concomitant medications may be assessed over the phone.
- QOL questionnaires, using EORTC QLQ-C30 and liver-specific QLQ-HCC18, (Visits 3 through 6). The questionnaires may be administered over the phone, as needed.
- Pain score using the Numeric Pain Rating Scale (Visit 3 only). The questionnaire may be administered over the phone, as needed.
- Technique efficacy evaluation (Visit 3 only).
- Imaging to determine whether there has been a local or regional recurrence of lesion(s). If there is a recurrence, determine soft tissue liver lesion details via CT, MRI, PET, US, and/or X-ray.
 - All SOC scans of the abdomen/liver (CT, MRI, and/or PET) should be submitted to the Sponsor.
- Record relevant concomitant procedures (i.e. liver or lesion-related). Relevant concomitant procedures may be assessed over the phone.

- Record follow-up post-ablation treatment, including the number of successful repeat ablations, if applicable, and if patient has been hospitalized since the procedure. If patient has been re-ablated with NeuWave, record ablation procedure details as outlined in section 19.1, subsection 1.

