8.4.1 Primary Endpoint

Perioperative endpoint-

1. Technical success, defined as ablation of the target lesion(s) according to the protocol and covered completely, with an adequate margin, as defined by the performing physician (i.e., the ablation zone completely overlaps or

encompasses the target lesion(s) plus an ablative margin), as assessed by CT, MRI, PET, US, and/or X-ray, immediately following the procedure. Technical Success is assessed at Visit 2 following the ablation of the target lesion.

Short term endpoint -

2. Technique efficacy, ablation of the target lesion(s) according to the protocol and covered completely, with an adequate margin, as defined by the performing physician (i.e., the ablation zone completely overlaps or encompasses the target lesion(s) plus an ablative margin), as assessed by CT, MRI, PET, US, and/or X-ray, at Visit 3 (between 7 days and less than 3 months post-ablation).

Long term endpoint -

3. Target lesion recurrence (local recurrence) rate evaluated at every visit starting from visit 4 after the primary ablation at visit 2 of the target lesion(s), and overall evaluation at the 5-year follow-up, as assessed by CT, MRI, PET, US, and/or X-ray.

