8.4.2 Secondary Endpoints

Secondary endpoints of this registry are:

1. Secondary efficacy rate, defined as the percentage of soft tissue lesions that have undergone successful repeat ablations (target or non-target) following identification of local soft tissue lesion progression. A successful repeat ablation will be defined as ablation of the lesion according to the protocol and covered completely, with an adequate margin, as defined by the performing physician (i.e. the ablation zone completely overlaps or encompasses the lesion plus an ablative margin), as assessed by CT, MRI, PET, US, and/or X-ray, immediately following the procedure.

2. Regional recurrence rate at a separate location in the liver (outside the initial treatment site(s)), evaluated at every visit after ablation of the target lesion(s), and overall evaluation at the 5-year follow-up, as assessed by CT, MRI, PET, US, and/or X-ray.

3. Recurrence-free survival, evaluated at every visit after ablation of the target lesion(s), and overall evaluation at the 5-year follow-up, as assessed by CT, MRI, PET, US, and/or X-ray.

4. Overall survival, evaluated at every visit after ablation of the target lesion(s), and overall evaluation at the 5-year follow-up.
5. Assess economic impact of ablation by capturing procedure-related items such as: complete procedure duration, ablation duration, number of ablations, length of hospital stay, and number and types of probes used.
6. Incidence of adverse events (AEs) (SAEs) that are deemed at least unlikely related to the procedure or device and all serious adverse events (SAEs) from the start of the ablation procedure through the end of the study.
7. Two QOL questionnaires: European Organization for Research and Treatment of Cancer (EORTC) QLQ-C30 and liver-specific QLQ-HCC18.

Note: These two questionnaires were chosen as tools to assess overall health status/quality of life in the patient population with soft-tissue liver lesions.
8. Numeric Pain Rating Score.

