8.6 Analysis of Secondary Endpoints

The number and percentage of patients and lesions achieving secondary efficacy will be summarized and a two-sided 95% confidence interval will be provided based on Clopper-Pearson’s method. Analysis for secondary efficacy rate includes only repeat ablations for target and non-target lesions.

For patient level analysis – secondary efficacy is achieved for a patient when all re-ablations of target lesions and all re-ablations of non-target lesions are defined as a complete ablation by the performing physician. The denominator for subject level analysis will include subjects who had a re-ablation during visit 3 to visit 14 including unscheduled visits.

For lesion level analysis – secondary efficacy is achieved for a lesion when all repeat ablations of that lesion (target and non-target lesions) are defined as complete ablation by the performing physician. The denominator for lesion level analysis will include lesions that had a repeat ablation during visit 3 to visit 14 including unscheduled visits.

Regional recurrence rates will be estimated at patient level. Time-to-event analysis (survival analysis) using Kaplan-Meier’s method will be utilized to estimate the regional recurrence rate at 3-month, 6-month, up to 60-month follow up. Two-sided 95% CI will be estimated for regional recurrence rate. First occurrence of identification of a new lesion outside the initial treatment site(s) during visit 3 to visit 14 including unscheduled visits at patient level will be considered as the “event” for time-to-event analysis at patient level.

Recurrence-free survival rates will be estimated at patient level. Time-to-event analysis (survival analysis) using Kaplan-Meier’s method will be utilized to estimate the recurrence-free survival rate at 3-month, 6-month, and up to 60-month follow up. Two-sided 95% CI will be estimated for recurrence-free survival rate.

An “event” is defined for recurrence-free survival if any of the following conditions are met:

- a. First occurrence of a target lesion recurrence during visit 4 to visit 14 including unscheduled visits at patient level
- b. Identification of a new non-target lesion during visit 3 to visit 14 including unscheduled visits at patient level

c. Deaths from any cause of a patient during the follow up period

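### SAP 8.6 counts any repeat ablation from Visit 3 in the secondary efficacy rate, although the endpoint requires identified local progression first

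*SAP*

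**What the plan says.** SAP 8.4.2 defines secondary efficacy as "the percentage of soft tissue lesions that have undergone successful repeat ablations (target or non-target) following identification of local soft tissue lesion progression". Protocol 6.3 uses the same wording. Neither names a denominator.

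SAP 8.6 sets the analysis rule. Its scope sentence is "Analysis for secondary efficacy rate includes only repeat ablations for target and non-target lesions". For lesions: "The denominator for lesion level analysis will include lesions that had a repeat ablation during visit 3 to visit 14 including unscheduled visits". For patients: "The denominator for subject level analysis will include subjects who had a re-ablation during visit 3 to visit 14 including unscheduled visits". A lesion succeeds when every repeat ablation of it is judged complete by the operator. A patient succeeds when every re-ablation, of target and non-target lesions, is so judged. Progression appears in neither rule.

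Three other places bear on this:
- SAP 8.4.1 starts the evaluation of target lesion recurrence at Visit 4. Protocol 6.2 evaluates it at every visit after ablation.
- SAP 8.5 removes subjects who failed technique efficacy (assessed at Visit 3) from the recurrence analysis.
- Protocol 12.1 defines non-target lesions as those left out of the Visit 2 treatment, in fact or by plan.

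**The concern.** The endpoint is conditional on local progression; the analysis rule is conditional on having been re-ablated. These are different sets of lesions. A target lesion found incompletely treated at Visit 3 and ablated again has residual tumour, which the SAP handles as failed technique efficacy and not as recurrence. Under 8.6 that second ablation still counts toward secondary efficacy.

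The word *repeat* is also unclear for non-target lesions. By definition they were outside the Visit 2 treatment, so a first ablation during follow-up repeats nothing, and 8.6 does not say whether it is excluded.

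A second, separate matter is interpretation. Because only re-ablated lesions are counted, a progressed lesion that was resected, treated in another way or left alone is not in the rate. A reader could take the published figure as the share of local progressions rescued by ablation, which it does not estimate. SAP 8.7 plans no sensitivity analysis, so no alternative denominator would be shown.

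**Working it through.** The documents give no expected rate or lesion counts for this endpoint, so there is no plan figure to reproduce. All counts below are assumptions.

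**Notation.** *P* = locally progressed lesions (100 throughout); *R* = those re-ablated; *s* = their complete-ablation rate; *m* = lesions re-ablated without progression; *t* = their complete-ablation rate.

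- Rate under SAP 8.6: (R·s + m·t) / (R + m)
- Rate among lesions re-ablated after progression: s
- Rate over all progressed lesions: R·s / P

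**1. Effect of adding re-ablations without progression.** Subtracting the second rate from the first gives a shift of m/(R + m) × (t − s). Its sign is the sign of t − s.

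| R | s | m | t | SAP 8.6 | Re-ablated after progression | Shift (points) |
|---|---|---|---|---|---|---|
| 50 | 90% | 20 | 95% | (45+19)/70 = 91.4% | 45/50 = 90.0% | +1.4 |
| 80 | 90% | 20 | 95% | (72+19)/100 = 91.0% | 72/80 = 90.0% | +1.0 |
| 100 | 80% | 20 | 95% | (80+19)/120 = 82.5% | 80/100 = 80.0% | +2.5 |
| 40 | 80% | 40 | 95% | (32+38)/80 = 87.5% | 32/40 = 80.0% | +7.5 |
| 100 | 90% | 20 | 70% | (90+14)/120 = 86.7% | 90/100 = 90.0% | −3.3 |
| 40 | 90% | 40 | 70% | (36+28)/80 = 80.0% | 36/40 = 90.0% | −10.0 |

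When t = s the shift is zero.

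**2. Effect of leaving out progressed lesions that were not re-ablated.** With m = 0 and s = 90%, the 8.6 rate is 90% whatever share is re-ablated. Over all progressed lesions it is 0.90 × R/P:

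- 40% re-ablated: 36%
- 60%: 54%
- 80%: 72%
- 100%: 90%

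This omission can only raise the rate relative to the all-progressed figure or leave it equal.

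**3. Both together, with exact two-sided 95% Clopper-Pearson limits.** R = 60, s = 80%, m = 20, t = 95%:

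- SAP 8.6: 67/80 = 83.8% (73.8 to 91.1)
- Re-ablated after progression: 48/60 = 80.0% (67.7 to 89.2)
- All progressed: 48/100 = 48.0% (37.9 to 58.2)

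Here the first two intervals overlap widely, while the third lies below both.

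**The case against.** The best defence is that 8.6 implements 8.4.2, so *repeat ablation* there carries the progression condition with it. Protocol 17.9 leaves full analysis details to the SAP, and the SAP states its denominators openly. Nor is the Visit 3 start conclusive alone, since Protocol 6.2 allows recurrence to be found at that visit. This defence is possible, but 8.6 does not say it, and a programmer following 8.6 would include every repeat ablation. Within the SAP, counting target re-ablations from Visit 3 while evaluating target recurrence from Visit 4 points against silent inheritance.

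On omitted lesions the objection is stronger. The definition can be read as successes among lesions re-ablated after progression, and then leaving out the rest agrees with it. A denominator of all progressed lesions would also count resection, transplant or death before re-ablation as non-success, so it partly measures treatment choice in a registry that follows standard care. Both rates are legitimate.

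Three stronger readings that a reader might infer are not supported:

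- *The plan reports 91% where the true rate is 45%.* In the first row of the table, 45/100 = 45% over all progressed lesions does stand against 64/70 = 91.4%. Nearly all of that gap comes from the omission, which contradicts the definition on only one reading. The departure that holds on either reading moves the rate from 90.0% to 91.4%.
- *The patient-level rule is looser still and admits any later ablation.* The scope sentence in 8.6 limits the whole analysis to repeat ablations, and the patient-level success rule attaches re-ablation to lesions. What stands is that *repeat* is undefined for non-target lesions.
- *The denominator turns the endpoint into a second technical success rate.* The resemblance comes from the definition itself, which judges success by the operator's assessment immediately after the procedure. Changing the denominator would not alter that.

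**Conclusion.** The point holds in limited form. SAP 8.6 omits a condition that its own endpoint definition contains, so re-ablations of residual tumour without progression enter the rate at both lesion and patient level. The direction of the effect cannot be known in advance. Its size depends on how many such lesions there are and how their success compares, neither of which the documents give.

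The missing denominator in the definition is a choice to be made explicit, not a proven error. As 8.6 stands, the rate describes success among re-ablated lesions and should not be presented as how often progression is rescued by ablation. That distinction matters numerically whenever a sizeable share of progressed lesions is not re-ablated.

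This is one descriptive secondary endpoint with no hypothesis test (Protocol 17.5, SAP 8.4), so sample size and error rates are untouched. What is at stake is the meaning of a reported figure. It should be corrected before the final analysis.

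**What to change.** In SAP 8.6:

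1. Restrict numerator and denominator to lesions with local progression documented before the repeat ablation. State whether progression recorded at Visit 3 counts.
2. Keep the rule that all repeat ablations of the lesion must be complete.
3. At patient level, use patients with at least one such lesion, with success when all their repeat ablations of such lesions are complete.
4. Exclude first ablations of non-target lesions explicitly.
5. Alongside, report the proportion of all locally progressed lesions that had a successful repeat ablation, labelled as depending on treatment choice.
6. Report re-ablations without prior documented progression on a separate line. No data element listed in Protocol 12.3, 12.4 or 19.1 records the reason for re-ablation, so classify them from the recorded recurrence and technique efficacy assessments, and show a count of those that cannot be classified.

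The cost is SAP wording and some extra programming, with no new patient assessments. The main rate will rest on fewer lesions and so have a wider interval. The second figure will be no higher than the main rate, and lower whenever some progressed lesions were not re-ablated. Classification may be incomplete for retrospectively enrolled patients, for whom Protocol 14 accepts that assessments may not have been done.

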- Record all applicable AEs/SAEs and product complaints. Assessments for safety may be assessed over the phone.
- Record date of registry completion, when applicable.

Note: in the case a patient has a liver resection or liver transplant, he/she should continue to be followed in the study, as outlined per the study protocol. Post-ablation follow-up visits should occur as per site SOC.

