17.9 Analyses to be Conducted

Categorical variables will be summarized descriptively by frequencies and associated percentages. Continuous variables will be summarized descriptively by number of patients, mean, standard deviation, median, minimum, and maximum. Confidence intervals will also be provided for procedure-related variables.

Disposition of Registry Patients

Patient disposition will be summarized using counts and percentages. The number and percentage of patients completed and discontinued along with the specific reasons for discontinuation will be tabulated.

Demographic and Baseline Characteristics

Summary statistics will be provided for patient demographics and pre-operative ablation characteristics.

Primary and Secondary Endpoint Analyses

Regression analysis methodologies will be utilized to explore the relationship between dichotomous clinical outcomes (technical success, technique efficacy, and secondary efficacy rate) and ablation procedure, patient, and provider parameters. Time to event analyses will be used for target lesion recurrence, regional recurrence rate, recurrence-free survival, progression free survival, and overall survival.

Complete details regarding all analysis methodologies including approaches to handle multiple lesions per patient, variable selection techniques, data reduction techniques given the number of potential independent variables, as well as subgroup analyses of interest will be specified in the SAP.

The number and percentage of patients achieving technical success will be summarized and a 95% confidence interval will be provided. A similar summary will be provided for technique efficacy, as well as for the primary and secondary efficacy rates, as previously defined.

Target lesion recurrence rates at each post-ablation scheduled visit will be estimated using the Kaplan-Meier method and 95% confidence intervals will be provided. A similar summary will be provided for the 5-year overall rate. Similar summaries will also be provided for regional recurrence rate, overall and progression-free survival rates for the entire observation period from the ablation procedure date through 5 years of follow-up.

Scores from the EORTC QOL questionnaires and Numeric Pain Rating Scales will be summarized with methodology consistent to the recommendations of the specific survey. Additional endpoints will be summarized with descriptive statistics.

Plans for Interim Analysis

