1.2 Study Design

This is a multicenter, observational registry that follows patients for a total of up to 5 years from the date of the first liver ablation procedure with either the NEUWAVE Microwave Ablation System or the NEUWAVE Microwave Ablation System with Ablation Confirmation.

This is an “umbrella registry,” which was included as an optional component in other NEUWAVE studies; hence, data from consenting patients who are or will be enrolled in other NEUWAVE soft tissue liver lesion ablation studies will be included in this registry. All other patients will be enrolled and followed prospectively, enrolled retrospectively with prospective, longitudinal follow up, or enrolled retrospectively with all retrospective follow up.

2 Treatment Assignment

This is a single-arm registry where all enrolled patients will be ablated using the NEUWAVE Microwave Ablation System as part of the site’s SOC treatment or per protocol for those patients who are also enrolled in other NEUWAVE studies.

3 Randomization and Blinding Procedures

As this is a single-arm registry, no randomization will occur, and no blinding procedures are required.

4 Interval Windows

Interval windows are provided in the Schedule of Assessments section of the study protocol. No additional windows are planned for analysis purposes.

5 Levels of Significance

No levels of significance are specified as no specific hypotheses about any of the outcomes of interest are being formulated or tested. Two-sided 95% confidence intervals (CI) will be estimated for specific endpoints for descriptive purposes only.

6 Analysis Sets

All Enrolled Set (AES): Consists of subjects who signed informed consent form or retrospectively enrolled with a waiver for signing informed consent form. The AES will be used for disposition of study subjects.

Full Analysis Set (FAS): FAS Consists of subjects who met inclusion/exclusion criteria and to whom the NeuWave Ablation device was utilized during procedure. Primary and secondary endpoints will be analyzed using FAS.

Safety Analysis Set (SAF): SAF Consists of subjects who met inclusion/exclusion criteria and to whom the NeuWave Ablation device was utilized during procedure. Safety endpoints will be analyzed using SAF.

7 Sample Size Justification

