8.5 Analysis of Primary Endpoint

The number and percentage of patients and lesions achieving technical success will be summarized and a two-sided 95% confidence interval will be provided based on Clopper-Pearson's method. Technical success is achieved when the ablation is defined as a complete ablation by the performing physician. Technical success will be summarized at patient level and at lesion level. Technical success is achieved for a patient when all ablated lesions are defined as a complete ablation by the performing physician.

The number and percentage of patients and lesions achieving technique efficacy will be summarized and a two-sided 95% confidence interval will be provided based on Clopper-Pearson's method. Technique efficacy is achieved when the ablation is defined as a complete ablation by the performing physician. Technique efficacy will be summarized at patient level and at lesion level. Technique efficacy is achieved for a patient when all ablated lesions are defined as a complete ablation by the performing physician.

Target lesion recurrence will be summarized at patient level and at lesion level. Time-to-event analysis (survival analysis) using Kaplan-Meier's method will be utilized to estimate the target lesion recurrence rate at 3-month, 6-month, up to 60-month follow up. Cumulative incidence rate will be estimated for target lesion recurrence considering death as a competing risk and estimates will be presented at 3-month, 6-month, up to 60-month follow up. A two-sided 95% CI will be estimated for target lesion recurrence. Subjects who failed technique efficacy will be excluded from the analysis for target lesion recurrence.

First occurrence of a target lesion recurrence at patient level will be considered as the “event” for time-to-event analysis.

First occurrence of a target lesion recurrence at lesion level will be considered as the “event” for time-to-event analysis.

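### Regional recurrence is estimated by Kaplan-Meier alone, so its 5-year rate will overstate the share of patients who recur; add the death-competing cumulative incidence already planned for target lesion recurrence.

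*SAP*

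**What the plan says.** SAP 8.6 handles regional recurrence at patient level. Kaplan-Meier "will be utilized to estimate the regional recurrence rate at 3-month, 6-month, up to 60-month follow up", and "Two-sided 95% CI will be estimated for regional recurrence rate". The event is the first new lesion found away from the initial treatment sites, from Visit 3 to Visit 14 and at unscheduled visits. Death is not part of that event, and no other estimator is named.

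Protocol 17.9 is in line with this. After describing Kaplan-Meier for target lesion recurrence it says: "Similar summaries will also be provided for regional recurrence rate, overall and progression-free survival rates for the entire observation period".

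SAP 8.5 goes further for target lesion recurrence. It plans Kaplan-Meier and then adds: "Cumulative incidence rate will be estimated for target lesion recurrence considering death as a competing risk", at the same 3- to 60-month timepoints.

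Death enters two other analyses in SAP 8.6. Recurrence-free survival counts "Deaths from any cause of a patient during the follow up period" as an event, and overall survival has its own Kaplan-Meier estimate. SAP 8.7 plans no sensitivity analyses, and SAP 8.14 marks additional endpoint analyses as not applicable.

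**The concern.** The registry "follows patients for a total of up to 5 years from the date of the first liver ablation procedure", and some patients will die before any new liver lesion appears. A Kaplan-Meier analysis of a non-death event has one standard way to treat them: censor at death. Neither document says so in words, but nothing else in SAP 8.6 fits.

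One minus Kaplan-Meier then describes a population in which death is removed. A clinician or patient reading a 5-year regional recurrence rate will take it as the proportion of treated patients who develop a new liver lesion, and that is the cumulative incidence. The SAP makes this distinction for one recurrence endpoint and gives no reason for omitting it for the other. What is at stake is the size of a reported rate. No test or decision rule depends on it, but estimates are the registry's main product.

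**Working it through.** **No plan figure to reproduce.** The documents state no recurrence or death rate and no sample-size calculation (SAP 7). All hazards below are assumptions. The 5-year horizon comes from SAP 1.2, and the estimators come from SAP 8.5 and 8.6.

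**Direction.** Let S_r be the Kaplan-Meier curve for recurrence with deaths censored, S_d the corresponding curve for death without recurrence, and Λ_r the cumulative cause-specific hazard of recurrence.

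- One minus Kaplan-Meier: ∫ S_r dΛ_r
- Cumulative incidence: ∫ S_r·S_d dΛ_r

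S_d is never above 1, so one minus Kaplan-Meier is never below the cumulative incidence. They are equal only if nobody dies before recurrence.

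**Size.** With constant hazards r (regional recurrence) and d (death without it):

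- 1 − KM(t) = 1 − exp(−r·t)
- CIF(t) = r/(r + d) × [1 − exp(−(r + d)·t)]

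Central case, r = 0.20, d = 0.08, t = 5:

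- 1 − KM = 1 − exp(−1.0) = 63.2%
- CIF = (0.20/0.28) × [1 − exp(−1.4)] = 0.714 × 0.753 = 53.8%
- Excess = 9.4 percentage points

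The same formulas over the assumed grid at 5 years:

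| r per year | d per year | 1 − KM | CIF | Excess (points) |
|---|---|---|---|---|
| 0.10 | 0.05 | 39.3% | 35.2% | 4.2 |
| 0.10 | 0.12 | 39.3% | 30.3% | 9.0 |
| 0.20 | 0.05 | 63.2% | 57.1% | 6.1 |
| 0.20 | 0.08 | 63.2% | 53.8% | 9.4 |
| 0.20 | 0.12 | 63.2% | 49.9% | 13.3 |
| 0.30 | 0.05 | 77.7% | 70.8% | 6.9 |
| 0.30 | 0.12 | 77.7% | 62.7% | 15.0 |

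The extremes lie at the corners: 4.2 and 15.0 points.

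**Timing.** In the central case the gap is 18.1% against 17.4% at 1 year (0.7 points), 45.1% against 40.6% at 3 years (4.5 points) and 9.4 points at 5 years. The late timepoints are hit most.

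**A second parametrisation.** Set 5-year net recurrence at 30%, 50% or 70% and 5-year net death at 20%, 40% or 60%, converting each to a constant hazard by −ln(1 − p)/5. The excess runs from 2.9 points (30.0% against 27.1%) to 20.0 points (70.0% against 50.0%).

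**Transplant and resection.** Assume r = 0.10, d = 0.08 and a transplant hazard of 0.05 per year, with no recurrence possible once the site is removed. The true 5-year probability is (0.10/0.23) × [1 − exp(−1.15)] = 29.7%. Keeping transplanted patients in the risk set of the cumulative incidence also gives 29.7%, because they add survivors with no events, which is what happens to them. Treating transplant as a competing event gives 29.7% again. Only censoring at transplant departs from it: (0.10/0.18) × [1 − exp(−0.90)] = 33.0%.

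**The case against.** **The endpoint is secondary and descriptive.** SAP 5 and 8.4 rule out hypothesis tests, and SAP 8.6 follows the Kaplan-Meier summary in Protocol 17.9. Patients expected to live less than a year are excluded, and the 1-year gap in the central case is under 1 point. All of this stands and limits the severity. It does not remove the 5-year discrepancy.

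**Deaths are visible elsewhere.** Recurrence-free survival counts them and overall survival is reported. That is true, but one is a composite and the other ignores recurrence. The probability of regional recurrence cannot be recovered from the two.

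**Stronger readings that the documents do not support.**

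- *The Kaplan-Meier figure is not a probability.* It is a valid net probability if death and recurrence are independent. It answers a different question from the one most readers will ask.
- *The two recurrence rates cannot be compared.* SAP 8.5 also plans Kaplan-Meier for target lesion recurrence at the same timepoints and at patient level, so a like-for-like comparison exists. The risk is that a reader sets the regional Kaplan-Meier figure beside the target lesion cumulative incidence.
- *Patients stay at risk after transplant, and this biases recurrence.* Protocol 12.3 says "in the case a patient has a liver resection or liver transplant, he/she should continue to be followed in the study", which governs follow-up and not the risk set. The SAP is silent on the risk set. If the removed site cannot recur, keeping such patients at risk in the cumulative incidence gives the right probability, as the working shows. An added competing event would change nothing for target lesions. For regional recurrence it would drop later lesions that meet the SAP's event definition, which is a change of estimand.

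**Conclusion.** The point holds for regional recurrence and for death. With Kaplan-Meier as the only estimator, the reported rate will be at or above the real-world probability at every timepoint, and most clearly at 5 years. The direction needs no assumption beyond the default censoring of deaths, which is inferred from the method and event definition.

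The size rests on assumed constant hazards: 63% against 54% in the central case, and about 4 to 15 points over recurrence 0.10 to 0.30 and death 0.05 to 0.12 per year. Lower mortality would shrink the gap and higher mortality would widen it.

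This should be fixed, but it does not threaten the registry's primary endpoints. There is no finding of bias from the handling of transplant or resection. The only gap there is that the SAP does not state its rule.

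**What to change.** In SAP 8.6:

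1. Estimate regional recurrence by the Aalen-Johansen cumulative incidence with death as a competing event.
2. Report it with its two-sided 95% confidence interval at 3 to 60 months as the regional recurrence rate.
3. Keep the Kaplan-Meier estimate as supportive, labelled as a net probability with deaths censored. This also preserves the summary promised in Protocol 17.9.
4. Optionally, add one sentence saying that patients are not censored at liver transplant or resection in the cumulative incidence analyses.

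The cost is SAP wording and a small amount of programming, since SAP 8.5 already requires the same estimator. No new data are needed: death is recorded at study discontinuation. SAP 8.1 waives an amendment only for changes that leave the methodology alone, so this one needs an amendment, best made before the database lock that precedes the final analysis.
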